## 1 List of Abbreviations

PTSD = Posttraumatic stress disorder; STAIR = Skills training in affective and interpersonal regulation; EBT = Evidence-based treatment; CPT = Cognitive processing therapy; PE = Prolonged exposure; VHA = Veterans health administration; I-STEP = Implementing a skills training evidence-based treatment for PTSD; IBH = Integrated behavioral health; RCT = Randomized control trial; DSM-5 = Diagnostic and Statistical Manual of Mental Disorders, 5th edition; LEC-5 = Life events checklist for the DSM-5; PCL-5 = PTSD checklist for the DSM-5; RA = Research assistant; CAB = Community advisory board; PI = Principal investigator; CSQ-8 = Client satisfaction questionnaire, 8-item; ISEL-12 = Interpersonal support evaluation list, 12-item; BSI-18 = Brief symptom inventory, 18-item; CFIR = Consolidated framework for implementation research; LIM = Level of integration measure; ICS = Implementation climate scale; EBPAS-15 = Evidence-based practice attitude scale, 15-item; ORCA = Organizational readiness to change assessment; PCIS = Perceived characteristics of intervention scale

## 2 Protocol Summary

Title:	Implementing a Skills Training Evidence-Based Treatment for Posttraumatic Stress Disorder (ISTEP)
Population:	Adult primary care patients with posttraumatic stress disorder symptoms, N=60
Intervention:	Behavioral health interventions, including web-administered and clinician administered brief Skills Training in Affective and Interpersonal Regulation (STAIR) for PTSD
Objectives:	Hybrid type 1 effectiveness-implementation trial to assess the feasibility, acceptability, and preliminary effectiveness of web-versus clinician-administered brief STAIR (primary outcome: PTSD symptoms, secondary outcome: functioning) while gathering information on implementation of both modalities. Findings will inform a full stepped-care approach to PTSD treatment that spans primary care and specialty care.
Design/Methodology:	60 patients were randomized, 30 in each condition (webSTAIR v. Brief STAIR). Participants completed study survey assessments at baseline (0 weeks), 15 weeks (active treatment), and 9-months post-randomization. To ensure consistency in timing of data collection, assessments are not linked to condition or amount of content completed.
Subject Participation Duration:	9 months

### 3 Background/Rationale & Purpose

#### 3.1 Background Information

Provide background information, study rationale, and purpose / study objective(s) and/or hypotheses for this study. PTSD is a significant public health challenge that disproportionately affects individuals receiving care safety net hospitals. The lifetime prevalence of exposure to interpersonal violence among patients seen in safety net primary care and behavioral health clinics may be as high as 94%, with current diagnosis of PTSD ranging from 33% to 46%. Despite high rates of trauma and PTSD in these settings, PTSD is vastly under-recognized and under-treated, with only 13% of individuals with PTSD receiving any form of mental health treatment. Of those who do access treatment, only 57% receive a minimally adequate dose of psychotherapy (defined as at least 4 hours of therapist contact).

Racial, ethnic, and socioeconomic disparities in access to and retention in EBTs for PTSD can also be understood in terms of system- and client-level factors. At the system-level, low-income racial and ethnic minority individuals are more likely to live in neighborhoods with few mental health specialists. Further, providers in these settings have less access to specialized training in EBTs for PTSD, thereby rendering EBTs largely unavailable to clients. Clients in resource constricted communities are also more likely to access services through non-specialty primary care setting or community service agencies, and less likely to access specialty outpatient mental health services. These differences may reflect the pragmatic response to the low availability of mental health specialists and perceptions of lower quality of care, as well as consumer preferences for non-traditional mental health service settings. Preferences for informal support and non-specialty care may also be related to experiences of mental illness stigma and negative experiences with prior mental health treatment (including racial discrimination). The unavailability of EBTs for PTSD in usual care and underutilization of outpatient specialty care have led to concerning inequities in quality of care.

Stepped care service delivery models are one approach to making PTSD treatment more accessible, equitable, efficient, and cost-effective. Stepped care approaches usually begin with interventions that are more convenient or acceptable to clients, and, if indicated, progress to more intensive care. By comparison, standard delivery systems often have one mode of treatment that demands intensive therapist time. Despite promise from a recently piloted stepped care approach to treating PTSD in children, stepped care models that include EBTs for PTSD at Step 1 have not been developed for adults. Existing first-line EBTs for PTSD, such as Cognitive Processing Therapy (CPT) and Prolonged Exposure (PE) require specialized and intensive therapist training and consist of 10 to 12 60- or 90-minute sessions. Despite strong support for the effectiveness of these treatments, access to training, supervision, and consultation is largely unavailable to community providers. Implementation trials suggest that the most consistent barrier to implementing EBTs is the lack of time to provide the intervention within their existing clinical system. Given these concerns, clinical researchers in the U.S. have advocated for the development of a stepped care approach that begins with brief, convenient, and patient-centered interventions for PTSD.

This study will be conducted in compliance with the protocol, applicable regulatory requirements, and policies and procedures of the Boston Medical Center and BU Medical Campus Human Research Protection Program.

#### 3.2 Rationale and Purpose

Skills Training in Affective and Interpersonal Regulation (STAIR) is a safe, evidence-based intervention for PTSD that has been tested in specialty care and community-based settings, and has demonstrated effectiveness in improving PTSD symptoms. Both synchronous in-person /telehealth delivery and asynchronous web delivery (webSTAIR) have shown similar effect sizes in PTSD and depression symptom reduction (Bauer et al., in press; Jain et al., 2020).

## 4 Objectives

### 4.1 Study Objectives

Our objective is to support the implementation of STAIR in BMC General Internal Medicine and Family Medicine as the new standard of care. The intervention will be delivered by usual care therapists in the integrated behavioral health practice. Participants who enroll in the study will be randomized to either in-person/telehealth STAIR or webSTAIR. Those who do not enroll in the study will still be able to receive STAIR in person or via telehealth as part of usual care. We hypothesize that offering a low intensity treatment for PTSD (i.e., STAIR) through primary care will improve access to and engagement in care for PTSD among BMC's patient population.

This study will also allow us to compare the feasibility of two modes of treatment delivery (inperson/telehealth v. webSTAIR), while gathering further evidence of the effectiveness of the intervention in our local setting. We hypothesize that both formats will be effective in reducing mental health symptoms, while webSTAIR may have some advantages in regard to uptake and long-term sustainability in usual care.

### 4.2 Study Outcome Measures

Our evaluation will include a collection of both process measures to understand feasibility, acceptability, and satisfaction to help us make iterative improvements, and outcome measures to understand whether the treatment is improving patient PTSD symptoms, other mental health symptoms, and overall functioning as expected. Our evaluation will also rely on medical record data to evaluate healthcare utilization. All participants will be given a code that will be used on all data collection tools. The master key that connects participant codes to name, date of birth (DOB), contact information, MRN, and scheduled appointment date and time will be kept in a password protected word file saved on the password protected BMC Psychiatry network drive. The list will only be accessible to [name] and study team staff.

Participants' medical records will be accessed to obtain information about session scheduling, information about ongoing treatment at BMC, and other healthcare utilization data from 6 months pre-enrollment to 9 months from baseline. Participants will be asked to sign a medical release form in the case that they move out of the area during the study or attend visits at a different hospital, so that we may obtain medical records from their new hospital/doctor. In addition, we will obtain the list of EPIC encounters of each enrolled patient in order to keep track of number of scheduled/attended/no-showed appointments. In total, the following information will be extracted from participant medical records: MRN, Name, DOB, problems lists, and encounter data (date and time of scheduled appointments, and date and time of unscheduled care [i.e., emergency department visits, urgent care visits, Boston

Emergency Services Team (BEST) safety evaluations, records of hospitalization]). Participants will be informed of this extraction during the informed consent process.

#### 4.2.1 Primary Outcome Measures

**Feasibility and Acceptability.** We operationalized feasibility as participant retention and provider adherence to the protocol. Retention was calculated as the proportion of content for the assigned intervention that the participant completed (e.g., number of sessions [Brief STAIR] or number of modules [webSTAIR] completed / total number of sessions [5] or modules [10]). We utilized a researcher-developed fidelity checklist, adapted from the Brief STAIR fidelity checklist ([name] et al., 2002) to assess adherence to the intervention. Adherence is reported as percentage of session components delivered per protocol. Overall study fidelity was calculated at study completion based on adherence scores from a random 20% of Brief STAIR sessions. Fidelity was assessed by two raters. We assessed client acceptability (satisfaction) using The Client Satisfaction Questionnaire (CSQ-8, Larsen et al., 1979), an eight item self-report measure. Each item is scored on a 4-point Likert scale from 1 “poor” to 4 “excellent” to indicate level of satisfaction with services. Higher scores indicate greater satisfaction with services.

**Preliminary Effectiveness, PTSD Symptoms.** We use the PCL-5 to assess PTSD symptoms. The PCL-5 includes 20 items, which map onto DSM-5 criteria for PTSD. Items are scored on a 5-point Likert scale to indicate symptom severity (0 – not at all to 4 – extremely), with a possible total score of 0-80. A score  $\geq 33$  is considered clinically elevated.

#### 4.2.2 Secondary Outcome Measures

**Social and Emotional Functioning (Secondary outcome):** We use the Interpersonal Support Evaluation List (ISEL-12) to assess social functioning and the Brief Symptom Inventory (BSI-18) to assess general mental health functioning.

#### 4.2.3 Exploratory Outcome Measures

Changes in patterns of healthcare utilization is assessed via chart review from 6 months pre-treatment to 6 months post-treatment. We extract variables from the medical record including number of visits, visit types/departments, no-shows, etc. to characterize healthcare utilization.

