### 5 Study Design

I-STEP is a single site, unmasked, hybrid type 1 effectiveness-implementation trial which will assess the feasibility, acceptability, and preliminary effectiveness of Brief STAIR and webSTAIR while gathering data on implementation. We will randomize 60 patients (30 in each condition). Participants will complete study survey assessments at baseline (0 weeks), 15 weeks (active treatment), and 9-months post-randomization (follow-up; see Figure 1). To ensure consistency in timing of data collection, assessments are not linked to condition or amount of content completed. We hypothesize that: 1) Brief STAIR and webSTAIR will be effective in reducing PTSD symptoms (primary effectiveness aim) and mental health symptoms (secondary effectiveness aim); 2) Brief STAIR (clinician-administered) will have advantages

over webSTAIR (self-directed) in terms of treatment completion; and 3) webSTAIR will evidence advantages over Brief STAIR in regard to scalability and sustainability. Outcomes will be assessed using survey data and chart extraction.

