### *Web-administered STAIR (webSTAIR)*

Participants randomized to webSTAIR complete the program at their own pace. WebSTAIR includes the same content as Brief STAIR in ten online modules, which include audio, video, and text delivery of psychoeducation and therapy components, with interactive exercises to assist in skills practice. All webSTAIR participants will have a therapist on record for treatment oversight (in case higher-level of care is needed) and for treatment planning purposes. In some cases, webSTAIR participants will have access to their study therapists for sessions outside of this treatment, i.e., support that is not PTSD-specific. This may include regular therapy sessions (which typically occur every 4-6 weeks in usual care), but *not* Brief STAIR or other trauma-focused therapies during the treatment window. The RA provides patients with unique login information, technology support, and lightly encourages engagement through biweekly reminder phone calls/texts. The principal investigator (PI) and RA have access to administrator-level login, which allows them to access behavioral data on participant progress (time spent, modules completed). To protect patient privacy, open text fields within webSTAIR (e.g., personal written answers to exercises and modules) are not viewable by study staff. Patients have access to the program for all 9 months of study participation, though progress is only reported back to study therapists during the active treatment phase (weeks 0-15).

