We will collect participant data for 9 months from baseline. Treatment plans will continue to be determined by usual care providers, the study has no involvement in any decisions regarding care. This means that a participant's IBH therapist can continue the therapy, offer a different treatment option, or refer to other services at any time in the study and after the study is completed. At any time, patients can also choose to change their treatment plans, for example from webSTAIR to in-person/telehealth STAIR, or to another treatment option in the clinic. Access to webSTAIR will be discontinued at 9 months.

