## 15 Statistical Plan

### 15.1 Study Hypotheses

Hypotheses:

- A. Brief STAIR will lead to significant change PTSD symptoms between baseline and 3 months.
- B. WebSTAIR will lead to significant change PTSD symptoms between baseline and 3 months.
- C. There will be no group differences in change in PTSD across conditions.

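### Under the 15-week treatment phase, chart extraction stops about two weeks before the exploratory utilization outcome's 6-month post-treatment window ends

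*Combined protocol and SAP*

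**What the plan says.** Section 4.2.3 (Exploratory Outcome Measures) anchors the outcome to treatment: "Changes in patterns of healthcare utilization is assessed via chart review from 6 months pre-treatment to 6 months post-treatment". It lists visit numbers, visit types or departments, and no-shows as the variables.

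Section 4.2 anchors the data to enrollment and baseline instead, with extraction of "other healthcare utilization data from 6 months pre-enrollment to 9 months from baseline". The chart-extraction paragraph of Section 12 repeats this span, and the study design schedule there adds: "We will collect participant data for 9 months from baseline".

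Section 5 sets the assessments at "baseline (0 weeks), 15 weeks (active treatment), and 9-months post-randomization" and refers to the two later ones as the post-treatment and follow-up assessments. The webSTAIR part of Section 8 also gives the active phase as weeks 0 to 15, although "Patients have access to the program for all 9 months of study participation". Section 15.1 uses another time point: "Brief STAIR will lead to significant change PTSD symptoms between baseline and 3 months".

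Section 15.3 describes t-tests for pre-to-post and pre-to-follow-up differences, and mixed models for the study outcomes across time points. It does not mention change in utilization, a rate per unit of time, or how weeks 0 to 15 are to be treated. Counts of behavioral health encounters appear there only as an indicator of engagement.

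**The concern.** The outcome window and the extraction window start from different dates, and under the 15-week active phase they do not fit together. The last part of the stated post-treatment period lies beyond the last record extracted. A comparison of visit counts then sets a shorter period against a longer one, and the shorter one is the later. That produces an apparent fall in visits with no change in behaviour. Section 6.3 gives reduced utilization as something the study expects to be able to assess, so the artefact points the expected way.

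The silence of Section 15.3 leaves a second possibility open. If the treatment weeks were counted in the later period, it would be longer than the earlier one and would include assigned Brief STAIR sessions in one arm.

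**Working it through.** **Inputs**
- Outcome window: 6 months before to 6 months after treatment (Section 4.2.3).
- Records: 6 months before enrollment to 9 months from baseline (Sections 4.2 and 12).
- Active treatment: weeks 0 to 15, or 15 × 7 = 105 days (Sections 5 and 8).
- Other candidate time point: 3 months (Section 15.1).
- Brief STAIR: five sessions, interval not stated (Section 8).
- Assumptions: one month = 365.25/12 = 30.4375 days; baseline and randomisation fall on the same day.

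**Can the stated 6 months be reproduced?** Months available = 9 − end of treatment.
- Treatment ending at 3 months: 9 − 3 = 6.00 months. The stated figure is reproduced exactly.
- Treatment ending at week 15: 9 × 30.4375 = 273.9 days; 273.9 − 105 = 168.9 days; 168.9/30.4375 = 5.55 months. It is not reproduced.

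**Size of the gap at week 15**
- Needed: 105 + 6 × 30.4375 = 105 + 182.6 = 287.6 days.
- Short by 287.6 − 273.9 = 13.7 days, and 13.7/182.6 = 7.5% of the window.
- Observed share: 5.55/6 = 92.5%. With a constant visit rate, the raw count after treatment is 0.925 of the count before, an apparent fall of 7.5%.

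**Dependence on when treatment ends.** A full 6 months exists only if treatment ends by 3 × 30.4375 = 91.3 days, or week 13.04. The documents fix no individual end date, so the weeks below other than 15 are illustrative.

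| End of treatment | Post-treatment months on record |
|---|---|
| Week 10 | 6.70 |
| Week 13 | 6.01 |
| Week 15 | 5.55 |
| Week 17 | 5.09 |
| Week 19 | 4.63 |

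If the whole webSTAIR access period counted as treatment, nothing would be left (9 − 9 = 0).

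**If weeks 0 to 15 were counted in the later period**
- Length ratio: 9/6 = 1.5, so raw counts rise 1.5-fold at an unchanged rate. A true 20% reduction would show as 0.8 × 1.5 = 1.2, a 20% increase.
- Up to five assigned sessions would add 5/9 = 0.56 visits per month in the Brief STAIR arm.

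These two figures belong to a different reading from the 7.5% and should not be added to it. If the later period starts at week 15, sessions held in weeks 0 to 15 fall outside it.

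**The case against.** The strongest reply is that Section 4.2.3 never defines the end of treatment. The hypotheses use 3 months, and 3 + 6 = 9 matches the extraction limit exactly. Brief STAIR has five sessions and webSTAIR is self-paced, so some participants will finish by about week 13 and be fully covered. This stands in part. It rules out the inference that the outcome cannot be built, or that the window is never fully observed: even at week 15, 92.5% of it is there. It does not remove the mismatch. Section 15.1 concerns PTSD symptoms, no assessment is scheduled at 3 months, and Section 5 ties post-treatment to the 15-week assessment. Individual end dates would make the length of follow-up depend on pace, and possibly on arm.

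A reader might also infer that 9 months of counts will be compared with 6. The documents do not say so. The definition in Section 4.2.3 is symmetric, and extracting a wider span than the outcome needs is ordinary practice. The 1.5-fold figure and the session imbalance are therefore conditional. What remains is that Section 15.3 contains nothing to exclude that comparison.

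Nor do the documents support a claim that only one arm can have such visits. Section 12 lets participants move from webSTAIR to clinician-delivered STAIR, and Section 8 allows webSTAIR participants other sessions with their therapist. Recording visit types already permits some separation.

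Finally, the stakes are low: the outcome is exploratory, and no hypothesis in Section 15.1 concerns utilization. That is correct and limits the weight of the point.

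**Conclusion.** The point holds as a mismatch of modest size. With active treatment ending at week 15, the extracted records cover 5.55 of the stated 6 post-treatment months, 13.7 days or 7.5% short. Raw counts would show a fall of about 7.5% at an unchanged rate. That could reverse the sign only of a true increase small enough to be masked by it, so a general claim of wrong-sign results is not supported.

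The size rests on three assumptions: post-treatment means after week 15, raw counts are compared, and baseline and randomisation coincide. A treatment end by about week 13 removes the gap. A randomisation date later than baseline would widen it day for day, if treatment weeks run from randomisation while records stop 9 months from baseline. The pre-treatment side is covered provided treatment starts at or after enrollment.

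Primary and secondary conclusions are unaffected. It is still worth correcting, because the definition does not match the data and the correction is cheap.

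**What to change.** Reconcile Sections 4.2, 4.2.3, 12 and 15.1 on when treatment is taken to end for analysis and on which dates bound the utilization periods. Then add to Section 15.3:
- Anchor all utilization windows at randomisation.
- Report visits per person-month in three periods that the records already cover: the 6 months before, weeks 0 to 15, and week 15 to month 9. A count model with a log person-time offset is one suitable option; for a descriptive outcome in 60 patients, tabulated rates may suffice.
- Report Brief STAIR sessions separately from all other visits, in both arms, so that the intervention is not read as a change in other care.

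The cost is analysis-plan wording and stating a post-treatment window of about 5.5 months instead of 6. No new extraction is needed. Keeping a full 6 months after week 15 would instead require records to day 287.6, about 9.5 months from baseline, which is beyond the stated extraction span.

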## 6.3 Analysis of Risks in Relation to Benefits

This study advances our ability to assess if PTSD treatment offered in IBH is actually helping reduce mental health outcomes and healthcare utilization as expected and will provide important information from patients about what might need to change in order to be more effectively implemented in this clinic. We believe the risks to participate are reasonable given the importance of direct clinical knowledge that is expected to result from the study.

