## 8 Study Intervention

### *Clinician-administered Brief STAIR*

Participants randomized to Brief STAIR complete five 30-minute sessions with a study therapist via telemedicine or in-person based on patient preference and Covid-19 restrictions in the setting. Brief STAIR is five sessions and includes all core elements of traditional 10-session STAIR. Each session begins with review of the patients' most recent PCL-5 score (documented in the medical record by the RA). Session 1 provides psychoeducation around the impact of trauma on emotions and relationships, an introduction to the treatment program structure, and a focused breathing exercise. Sessions 2-4 focus on emotion regulation skills across the body, thought, and behavior channels (i.e., the cognitive behavioral therapy triad). These include emotion regulation techniques such as focused breathing and emotion surfing to down-regulate symptoms of over-activation (e.g., anxiety, hyperarousal) and techniques such as behavioral activation and pleasurable activities planning to up-regulate individuals when they are in a depressive or dysthymic state. Session 5 focuses on compassion, strategies for improving social engagement and sustaining relationships (e.g., conflict resolution), review of treatment progress, and a plan to continue use of skills.

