password-protected, item-level and written content is not viewable outside of an individual account, and all information on the site is maintained in a confidential and secure manner. The VHA is not engaged in the same research project and will not have access to any study data collected by BMC (via RedCAP) for purposes of this study. They will not be able to link data gathered by webSTAIR to our data, as only BMC study team will know the link between webSTAIR usernames and Study ID numbers, and only the BMC study team will have access to data collected during study visits. webSTAIR is a password-protected website. For this study, we have been allocated a set of 30 patient-level accounts (with unique usernames and passwords) to distribute to study participants. In addition, the program manager has created four administrator-level account (2 for BMC study staff, including PI and RA; and 2 for VA collaborators). The administrator-level account allows study staff to see patient engagement information such as the date, time, and duration of accessing various modules on the website and optional self-assessments so patients can track their progress. The website does not collect item-level information (e.g., fillable text boxes within the modules and worksheets), this information is only available to patients via their unique login. The webSTAIR website does not communicate with the EMR. Because we will contact patients over the course of the study and will access patients' medical records, we will record their contact information, their date of birth, and their MRN. One list of names and contact information and Study IDs will be kept on a private password protected BMC network drive separate from any data collection tools and will only be accessible to the study team. All identifiable information will be transmitted, stored, analyzed, or otherwise exist only on HIPAA-compliant electronic systems that meet the standards for protection of PHI established by Boston Medical Center. As an extra layer of protection, we have a Certificate of Confidentiality because this project is NIH-funded.

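### If the utilization window includes active treatment, Brief STAIR sessions count as visits in one arm while webSTAIR modules do not, and the plan does not separate them

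*Combined protocol and SAP*

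**What the plan says.** Section 4.2.3 makes change in healthcare utilization an exploratory outcome, "assessed via chart review from 6 months pre-treatment to 6 months post-treatment", using "number of visits, visit types/departments, no-shows, etc. to characterize healthcare utilization". Section 4.2, repeated in Section 12, gives a different range for the extraction: "other healthcare utilization data from 6 months pre-enrollment to 9 months from baseline". The source is broad: "we will obtain the list of EPIC encounters of each enrolled patient in order to keep track of number of scheduled/attended/no-showed appointments". The same section shows that treatment sessions are looked up in the record: "Participants' medical records will be accessed to obtain information about session scheduling".

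On the treatments, Section 8 states that "Participants randomized to Brief STAIR complete five 30-minute sessions with a study therapist", and Section 4.1 has the intervention delivered by usual care therapists in the integrated behavioral health (IBH) practice. webSTAIR is ten self-paced online modules, and Section 14.1 notes that "The webSTAIR website does not communicate with the EMR".

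Section 6.3 gives the expected direction, describing PTSD treatment as "helping reduce mental health outcomes and healthcare utilization as expected". Section 15.3 examines time, group and time-by-group effects for all study outcomes, without saying whether utilization is one of them.

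**The concern.** The outcome is meant to show how patients' use of care changes, but the count as defined can include the randomized treatment itself. A Brief STAIR participant who attends every session gains visits by complying, and one who misses sessions gains no-shows. A webSTAIR participant who finishes every module gains neither. No section excludes, flags or separately tabulates the assigned sessions for this outcome.

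Two misreadings could follow. A real fall in other care could be masked in the Brief STAIR arm. And webSTAIR could appear to lower utilization only because its modules are not visits. Section 5 already expects webSTAIR to do better on scalability and sustainability, so an artefact in that direction could be taken as support.

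**Working it through.** The plan states no utilization figure, so there is nothing to reproduce. The check covers what falls in the count, how large the built-in difference could be, and what can be said about its consequences.

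**1. Are sessions in the count?** Section 4.1 (delivery by IBH therapists) and Section 4.2 (session scheduling read from the record) imply that each session is a medical-record encounter. No sentence says so. This is an assumption, though the natural one.

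**2. Does the window include treatment?** Active treatment is weeks 0–15 (Section 8).
- Sections 4.2 and 12: a continuous range to 9 months from baseline, so weeks 0–15 are inside.
- Section 4.2.3, read as one continuous range: 15 weeks is 15 × 7 / 30.44 = 3.4 months, and 3.4 + 6 = 9.4 months from baseline. Weeks 0–15 are inside, and the end point differs slightly from 9 months.
- Section 4.2.3, read as a before-treatment period compared with an after-treatment period: weeks 0–15 are in neither, and most sessions drop out.

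The text does not settle which reading is meant.

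**3. Built-in visits if weeks 0–15 are included.** Added visits per Brief STAIR participant = 5 × share completed. Completion shares are assumed: 40% gives 2, 60% gives 3, 80% gives 4 and 100% gives 5. The ceiling for the arm is 30 × 5 = 150. webSTAIR modules add 0.

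**4. Offset.** Section 8 allows some webSTAIR participants regular therapy visits, typically every 4–6 weeks. Over 15 weeks that is 15/6 = 2.5 to 15/4 = 3.75 visits. Suppose every webSTAIR participant had these and no Brief STAIR participant did:
- at full completion, the net gap is 5 − 2.5 = 2.5 down to 5 − 3.75 = 1.25 visits;
- at 60% completion, it is 3 − 2.5 = 0.5 down to 3 − 3.75 = −0.75, so it could vanish or reverse.

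Format changes, which Section 12 permits at any time, would alter it further. Section 8 rules out Brief STAIR for webSTAIR participants during the treatment window; those two statements must be reconciled.

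**5. Labelled illustration only.** The documents give neither an SD for visit counts nor an alpha. Assume two-sided alpha 0.05, 30 per arm, a normal approximation and no true effect on other care. The chance of a significant excess in Brief STAIR is then Φ(gap / (SD × √(2/30)) − 1.96).

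| Gap (visits) | SD 5 | SD 10 | SD 15 |
|---|---|---|---|
| 5 | 97% | 49% | 25% |
| 1.25 | 16% | 7% | 5% |

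The spread shows that the documents cannot fix a probability.

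**The case against.** The strongest reply is that the window decides the matter. Section 5 uses the term post-treatment for the assessment that follows baseline and precedes follow-up, that is, week 15. On that usage Section 4.2.3 may compare the 6 months before treatment with the 6 months after it, and the range in Section 4.2 may only limit chart access. This stands as a possible reading: a reader might infer that the problem exists under any window, and the documents do not support that.

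A reader might also infer a relative size. Over about 39 weeks after baseline, a visit every 4–6 weeks gives 39/6 = 6.5 to 39/4 = 9.75 visits, so 5 sessions would add 51% to 77%. But that cadence describes regular therapy visits only. The outcome covers all visit types and departments, and no total is given, so this is not a percentage of the outcome.

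Next, STAIR is described as a new standard of care, so its sessions are real use of services. If they replace ordinary therapy visits, removing them while keeping webSTAIR participants' therapy visits would bias the comparison the other way. This also stands, and it rules out using the STAIR-excluded count as the only headline.

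Finally, the stakes are limited. The outcome is exploratory, Section 4.2.3 aims to characterize patterns, no hypothesis in Section 5 or 15.1 names utilization, and Section 6.3 is risk-benefit text rather than an arm comparison. Visit types are extracted, and sessions are counted for retention. These points lower the weight of the concern, but none supplies a rule for separating sessions in this outcome. The additional contact hours in Section 15.3 do not supply one either: they are a covariate in post hoc symptom models.

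**Conclusion.** The point holds conditionally. If weeks 0–15 are in the window and sessions are recorded as encounters, the outcome as defined builds up to 5 attended visits per Brief STAIR participant, plus any no-shows for missed sessions, into the before/after and between-arm comparisons. webSTAIR modules add none. The net between-arm gap shrinks with regular therapy visits or format changes in the webSTAIR arm, and the problem largely disappears if weeks 0–15 are meant to be skipped.

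A reader might go further and infer that the trial is likely to report a spurious utilization difference. The documents do not support that: they contain no visit total, SD or completion rate, and the illustrative chances run from 5% to 97% on assumed inputs. The consequence is confined to interpreting an exploratory outcome. It is worth correcting because the correction is cheap.

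**What to change.** In Section 4.2.3:

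- State one window, say whether weeks 0–15 are included, and align it with Sections 4.2 and 12.
- Flag STAIR encounters and their no-shows by matching to the session records already kept for retention (Section 4.2.1) and fidelity (Section 8). Missed sessions leave no recording, so take these from the session-scheduling data already extracted. Do not rely on department or therapist alone, because the same therapists also give other visits.
- Report side by side: (a) all encounters; (b) encounters excluding STAIR sessions, with non-STAIR behavioral health visits shown separately so that any substitution is visible; (c) unscheduled care, which is already extracted.
- State that an arm difference or change in the all-encounter count alone will not be read as an effect on other care.

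The cost is a few sentences, a modest matching step and two or three extra table rows. No new data are needed from participants.
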